Reference Therapy:	Placebo [REDACTED]
Treatment Duration:	All subjects will receive the first dose of IP within 24 hours after stroke symptoms on Day 0 and will be hospitalized for the care of AIS according to each study site's current standard of care. Each subject will receive [REDACTED] LT3001 drug product or placebo via a 30-minutute intravenous infusion twice within every approximately 24 hours, total 6 doses of IP within approximately 72 hours.  The participation for each subject is approximately 92 days from the Screening (Visit 1) to the last visit.

Efficacy:	Efficacy will be evaluated by assessing the functional outcomes measured by mRS, neurological outcome assessed by NIHSS, the occurrence of recurrent stroke, and cognition assessed by the MoCA; and imaging outcomes measured by change in infarct volume and hypoperfusion lesion.
Safety:	Safety assessments include the occurrence of sICH, aICH, mortality, and AEs.

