## Overdose

The dose level of LT3001 drug product will be calculated by the Investigator or a qualified designee [REDACTED]. Because drug accumulation is not anticipated [REDACTED], and subjects will only receive LT3001 drug product administered by an Investigator or a qualified designee and under close monitoring, it is anticipated that the risk of overdose or medication error will be low.

Any overdose, with or without associated AEs, should be promptly reported by the Investigator or designee [REDACTED] Pharmacovigilance (see contact details in [Section 12.7.3](#)). Overdoses and medication errors will be documented as protocol deviations and communicated to the Study Monitor.

No specific therapy for overdose of LT3001 drug product exists. In the event of overdose or medication error, appropriate standard of care (SoC) therapy for the subject's symptoms and clinical status will be provided.

Details regarding known or anticipated benefits and risks, as well as reasonably anticipated AEs for LT3001 may be found in the investigator's brochure.

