## 12.7 Adverse Events

### 12.7.1 Adverse Events

An AE is any symptom, physical sign, syndrome, or disease that either emerges during the study if present on or after the 1st IP administration [REDACTED], worsens during the study, regardless of the suspected cause of the event. All medical and psychiatric conditions present [REDACTED] before the subject receives the 1st IP administration will be documented in the medical history eCRF. Changes in these conditions and new symptoms, physical signs, syndromes, or diseases should be noted on the AE eCRF during the rest of the study. Clinically significant laboratory abnormalities should also be recorded as AEs. Surgical procedures that were planned before the subject enrolled in the study are not considered AEs if the conditions were known before study inclusion; the medical condition should be reported in the subject's medical history.

Subjects will be instructed to report AEs during the study. All AEs are to be followed up until resolution or a stable clinical endpoint is reached.

Each AE is to be documented on the eCRF with reference to date of onset, duration, frequency, severity, relationship to IP, action taken with IP, treatment of event, and outcome. Furthermore,

each AE is to be classified as being serious or nonserious. Changes in AEs and resolution dates are to be documented on the eCRF.

For the purposes of this study, the period of observation for collection of AEs extends from the subject receives the 1st IP [REDACTED] until the last follow-up visit. Follow-up of the AE, even after the date of therapy discontinuation, is required if the AE persists, until the event resolves or stabilizes at a level acceptable to the Investigator.

When changes in the intensity of an AE occur more frequently than once a day, the maximum intensity for the event should be noted. If the intensity category changes over a number of days, then those changes should be recorded separately (with distinct onset dates).

Specific guidelines for classifying AEs by intensity and relationship to IP are given in [Table 3](#). and [Table 4](#).

Table 3. Classification of Adverse Events by Intensity

MILD: An event that is easily tolerated by the subject, causing minimal discomfort and not interfering with everyday activities.
MODERATE: An event that is sufficiently discomforting to interfere with normal everyday activities.

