4.1. Brief Description

This is a multicenter, double-blind, randomized, and placebo-controlled prospective Phase II clinical study, designed to evaluate LT3001 drug product versus placebo in subjects with AIS. The study is planned to take place in multiple countries. Subjects who participate in this trial should be treated with standard of care of AIS therapies when appropriate.

Approximately 200 eligible subjects will be randomized centrally 1:1 to LT3001 drug product or placebo with the stratification factors. Randomization will be stratified according to age [REDACTED], baseline NIHSS [REDACTED], and time of AIS symptoms onset to the 1st IP [REDACTED]

[REDACTED]

[REDACTED]

Each eligible subject will [REDACTED] The first dose of LT3001 drug product or placebo (1st IP) will be administered within 24 hours after stroke symptoms onset. [REDACTED]

[REDACTED]

LT3001 drug product or placebo will be administered [REDACTED].

A Data Safety Monitoring Board (DSMB) will be formed to assess all data (including imaging data) of LT3001 drug product or placebo treatment. [REDACTED] The DSMB will review safety and efficacy data when the thirtieth treated subject has completed study procedures on Day 7 or terminated the study before Day 7. The DSMB will meet after the data presentation and will issue recommendations relating to safety and study conduct. Unscheduled meetings will be recommended and initiated by the Sponsor or the Principal Investigators. [REDACTED]

[REDACTED]

[figure not shown]
[REDACTED]

[REDACTED]

The participation for each subject is approximately 92 days from the Screening (Visit 1) to the last visit.

This document is confidential.

Study Design

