5.2. Secondary Endpoints

Clinical efficacy outcomes:

1. Functional outcome

- a. The proportion of subjects achieve [REDACTED] mRS 0-1 [REDACTED]. The proportion of subjects achieve [REDACTED] mRS 0-2 [REDACTED].
- b. The proportion of subjects with independent functional outcome, defined as mRS ≤ 2 [REDACTED] after the 1st IP.
- c. The proportion of subjects with excellent functional outcome, defined as mRS ≤ 1 [REDACTED] after the 1st IP.
- d. The shift of proportion of subjects with each grade on mRS [REDACTED] [REDACTED] from Baseline.

2. Neurological outcome

- a. The National Institute of Health Stroke Scale (NIHSS) [REDACTED] [REDACTED] after the 1st IP [REDACTED].
- b. The proportion of subjects with neurological outcome improvement, defined as a decrease in NIHSS ≥ 4 points [REDACTED] from Baseline.
- c. The proportion of subjects with neurological outcome improvement, defined as a decrease in NIHSS ≥ 4 points or NIHSS of 0 to 1 point [REDACTED] [REDACTED] from Baseline.
- d. The proportion of subjects with NIHSS ≤ 2 [REDACTED] after the 1st IP.
- e. The proportion of subjects with NIHSS ≤ 1 [REDACTED] after the 1st IP.
- f. Change in NIHSS [REDACTED] from Baseline.

3. The occurrence of recurrent stroke within 90 days after the 1st IP.

4. The change of cognition assessment by Montreal Cognitive Assessment (MoCA) [REDACTED] from Baseline [REDACTED].

Imaging outcomes:

1. The change of infarct volume [REDACTED] from Baseline by magnetic resonance imaging (MRI)/computed tomography perfusion (CTP).
2. The change of hypoperfusion lesion [REDACTED] from Baseline by perfusion-weight imaging MRI/CTP.

This document is confidential.

3. The proportion of subjects with 90% reduction in hypoperfusion lesion [REDACTED] from Baseline by perfusion-weight imaging MRI/CTP.
4. The infarct volume [REDACTED] after the 1st IP by MRI/CTP [REDACTED].

Safety outcomes:

1. The occurrence of symptomatic intracranial hemorrhage (sICH) [REDACTED] after the 1st IP; clinical deterioration defined as an increase in the NIHSS of 4 points or more AND confirmed by MRI/CTP imaging – documentation.
2. The occurrence of asymptomatic intracranial hemorrhage (aICH) [REDACTED] after the 1st IP.
3. The occurrence of mortality due to any reason within 90 days after the 1st IP.
4. The number and severity of AEs within 90 days after the 1st IP.
5. The number of subjects with AEs within 90 days after the 1st IP.

This document is confidential.

6. Analysis Sets

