11.1. Primary endpoint

Proportion of subjects with AEs, judged to be probably or definitely related to the IP within 90 days after the 1st IP.

The number and percentage of subjects with AEs, judged to be probably or definitely related to the IP within 90 days after the 1st IP will be presented by treatment group on the Safety population. The difference of the proportions between the treatment groups with the corresponding exact 95% Clopper Pearson CIs will be presented.

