11.2.4. Adverse Events

An AE is any symptom, physical sign, syndrome, or disease that either emerges during the study or, if present on or after the 1st IP administration [REDACTED], worsens during the study, regardless of the suspected cause of the event. AEs are defined as Treatment-emergent adverse events (TEAEs) in the SAP and TLFs.

An SAE is any untoward medical occurrence, in the view of either the Investigator or Sponsor, that:

- results in death,
- is life-threatening,
- results in inpatient hospitalization or prolongation of existing hospitalization,
- results in persistent or significant disability/incapacity, and/or
- is a congenital anomaly/birth defect

Other important medical events that may not be immediately life-threatening or result in death or hospitalization, based upon appropriate medical judgment, are considered SAEs if they are thought to jeopardize the subject and/or require medical or surgical intervention to prevent one of the outcomes defining an SAE.

This document is confidential.

Also, Related TEAE is an any event deemed possibly, probably or definitely related to treatment.

All AEs will be coded using the actual version of MedDRA dictionary to provide the system organ class (SOC) and preferred term (PT). Duration of the adverse event (AE) will be calculated and presented in days. Duration of the AE is defined as (AE end date – AE start date) + 1.

The number and percentage of subjects as well as number of events will be presented for TEAE summaries. An overall summary of TEAEs including the following categories will be presented:

- at least one TEAE
- at least one serious TEAE
- at least one related TEAE
- at least one TEAE leading to study drug withdrawal
- at least one TEAE with fatal outcome

A summary table of TEAEs by SOC and PT will be presented. Multiple instances of the TEAE in each SOC and multiple occurrences of the same PT are counted only once per subject. The denominator used for calculating the percentages will be the total number of subjects included in the safety population.

In addition, for each of the following, a summary of TEAEs will be produced at the subject level:

- Serious TEAEs by SOC and PT
- TEAEs by worst intensity by SOC, PT
- TEAEs by maximum relationship by SOC, PT
- TEAEs leading to study drug withdrawal

All AEs for each subject, including multiple occurrences of the same event, will be presented in full in a comprehensive listing sorted by subject number.

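### SAP 11.2.4 lists no adverse-event table by onset period, so its all-cause 90-day subject counts dilute any excess arising around the roughly 72 hours of dosing

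*SAP*

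**What the plan says.** SAP 11.2.4 gives the definition: "AEs are defined as Treatment-emergent adverse events (TEAEs) in the SAP and TLFs". The visible text sets no upper time limit relative to the last dose.

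The two time scales come from elsewhere in the documents:

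- **Dosing.** The Protocol Synopsis (Treatment Duration) plans a "total 6 doses of IP within approximately 72 hours". Protocol 5.3 (Overdose) adds that "drug accumulation is not anticipated".
- **AE collection.** Protocol 12.7.1 says "the period of observation for collection of AEs extends from the subject receives the" 1st IP and runs "until the last follow-up visit. Follow-up of the AE, even after the date of therapy discontinuation, is required" if the event persists. SAP 4.1 fixes the length: "The participation for each subject is approximately 92 days from the Screening (Visit 1) to the last visit".

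The 90-day horizon is set by the protocol, not introduced by the SAP. The secondary safety endpoint repeated in SAP 5.2 reads "The number of subjects with AEs within 90 days after the 1st IP". The primary endpoint in SAP 11.1 uses the same horizon but filters on causality: "Proportion of subjects with AEs, judged to be probably or definitely related to the IP within 90 days after the 1st IP".

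SAP 11.2.4 then lists an overall TEAE summary and tables by SOC/PT, for serious TEAEs, by worst intensity, by maximum relationship, and for TEAEs leading to drug withdrawal. Subject counts and event counts are both required. No listed table is split by time of onset. SAP 11.2.1 and 11.2.2 give sICH and aICH their own sections, with time windows that are redacted.

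**The concern.** Safety is the primary objective, and the hazard suggested by the nonclinical work is acute. Protocol 5.2.1 describes falls in blood pressure and rises in heart rate in dogs, mini-pigs and monkeys, and in monkeys these resolved within hours. If the infusions provoke events, most of that excess should appear during or soon after dosing.

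The primary endpoint depends on investigators judging an event probably or definitely related. Under Protocol Table 4, the lower of those two categories calls for three of four criteria. The all-cause tables are the natural check on that judgement, because they compare arms without using causality. If each all-cause table runs to Day 90, subjects with a late pneumonia or another stroke complication are counted in both arms. A subject who would have had such an event anyway cannot add to the difference in the any-TEAE row, however clear the acute reaction was. The report could then show similar TEAE proportions in the two arms despite a real excess around dosing. Onset dates are listed by subject (Protocol 13.4.2), but a listing gives no rate or difference by arm.

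**Working it through.** The plan has no figure of its own to reproduce here. The sample-size sections (Protocol 13.1, SAP 4.3) are not visible, and no AE rate is stated for this trial. What follows is an illustration.

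**Inputs from the documents.** About 200 subjects at 1:1, so about 100 per arm (SAP 4.1). Dosing of about 3 days in a 90-day window: 3/90 = 3.3%.

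**Assumed inputs.** Acute (dosing-period) risks p_C and p_T. Late background risk q, equal in both arms and independent of the acute events.

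**Dilution.** 90-day risk = 1 − (1 − p)(1 − q), so the difference between arms is (1 − q)(p_T − p_C).

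**Yardstick.** Power = Φ[(d − 1.96·SE₀)/SE₁], where d is the risk difference. SE₀ is the pooled and SE₁ the unpooled standard error, with n = 100 per arm and two-sided 5%.

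For p_C = 10% and p_T = 25%:

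| q | Placebo | LT3001 | Difference (points) | RR | Power |
|---|---|---|---|---|---|
| 0 (dosing window only) | 10.0% | 25.0% | 15.0 | 2.50 | 80% |
| 20% | 28.0% | 40.0% | 12.0 | 1.43 | 43% |
| 50% | 55.0% | 62.5% | 7.5 | 1.14 | 19% |
| 70% | 73.0% | 77.5% | 4.5 | 1.06 | 11% |

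The q = 50% row in full: d = 0.075, SE₀ = √(2 × 0.5875 × 0.4125/100) = 0.0696, SE₁ = √((0.2475 + 0.2344)/100) = 0.0694. Then (0.075 − 0.1365)/0.0694 = −0.885, and Φ = 0.188.

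Other assumed acute risks behave alike at q = 20%, 50% and 70%. For 20% v 35%, power falls from 66% to 40%, 20% and 12%. For 5% v 15%, it falls from 66% to 24%, 11% and 7%.

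**Outputs filtered by causality.** If the filter lets through few late events (q = 2% to 5%), the 15-point difference becomes 14.7 to 14.3 points and power 76% to 69%. Little is lost.

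**What a cut-off would recover.** Suppose IP adds an AE in 15% of subjects, independent of background (all background rates assumed):

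| Window | Background | LT3001 arm: 1 − (1 − background)(0.85) | Difference (points) | Power |
|---|---|---|---|---|
| Day 90 | 85% | 87.3% | 2.3 | 7% |
| Day 7 | 45% | 53.3% | 8.3 | 21% |
| 72 hours | 25% | 36.3% | 11.3 | 41% |

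Over background ranges of 70–95%, 30–60% and 15–35%, power is 6–11%, 14–34% and 29–60% respectively.

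**Single preferred term, IP adding 8%.** A 10% background at 90 days gives 1 − 0.90 × 0.92 = 17.2% and power 32%. A 5% background gives 1 − 0.95 × 0.92 = 12.6% and about 47%. A 3% background gives 1 − 0.97 × 0.92 = 10.8% and 58%. Late events under other terms do not enter the row, so the loss is smaller.

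**The case against.** The strongest reply is that the SAP faithfully implements 90-day endpoints set by the protocol, and that much of the safety output is not exposed to this dilution. Most of that stands:

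- The primary endpoint, the related-TEAE row and the table by maximum relationship separate events by blinded causality, with temporal sequence among the criteria in Protocol Table 4. Late complications judged unrelated fall elsewhere.
- The withdrawal table is tied to dosing, because IP can be withdrawn only while the roughly 72-hour course is under way.
- sICH, aICH, vital signs and ECG have their own summaries.
- Event counts do not saturate: late events add noise but do not hide a subject's acute event.
- The serious-TEAE row is probably diluted less than the any-TEAE row. In the earlier single-dose stroke study (Protocol 5.3), SAEs occurred in 25.0% of each arm. Even if all were late, the factor would be 1 − 0.25 = 0.75. That study was small (4 and 2 subjects).

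A reader might go further and infer that the TEAE tables as a whole have almost no sensitivity to acute harm. The documents do not support that: near-saturation is plausible only for the any-TEAE row and perhaps broad SOC rows. Nor does an off-drug share of 87 of 90 days (97%) mean that 97% of events are late. It is a share of time, and AEs after acute stroke may cluster early. In the illustration above, 45 of the 85 background points fall by Day 7.

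The index of tables (SAP 18) is not shown and the shells are a separate document (SAP 21), so a table by onset period may exist. What the reply leaves standing is that the visible list in SAP 11.2.4, which does not appear redacted, calls for none.

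**Conclusion.** The point holds in limited form. As listed, the all-cause summaries that count subjects over 90 days understate an acute risk difference by the factor 1 − q: 20%, 50% or 70% of it is lost at q = 0.2, 0.5 or 0.7. The size rests on a late background rate that the documents do not give, and on independence of acute and late events. If subjects who react to the drug are also more prone to late complications, the loss is greater; if less prone, smaller. Power serves only as a yardstick, since SAP 8.1 declares all comparisons descriptive, but the estimated difference shrinks just the same.

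No error in the primary endpoint, sample size or type I error follows, and the TEAE definition need not be replaced. This is an inexpensive improvement to how the primary safety question is answered. Its gain should not be overstated: in the illustration, a Day 7 cut-off raises power for any TEAE only from 7% to 21%, and the larger figures belong to a shorter window.

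**What to change.** Leave unchanged the TEAE definition, the 90-day tables and endpoints, and the SAP 8.3 rule that counts a missing TEAE relationship as related. Narrowing the definition would disturb the 90-day tables and could take later events outside that rule.

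Before database lock, add to SAP 11.2.4 an overall summary and SOC/PT, serious and worst-intensity tables by arm and by onset period:

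1. From the 1st IP through a pre-specified short interval after the last dose. Day 7 is one option, stated as an analysis convention. In SAP 2.2, Day 7 only triggers the DSMB review of the first 30 treated subjects, so it cannot be cited as an established AE risk window. A shorter window would be more sensitive.
2. The remainder to Day 90.

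For at least one TEAE in the first period, give the difference in proportions with a 95% CI. SAP 8.3 assumes that AEs with missing or incomplete onset dates arose during study treatment unless the partial date shows otherwise, so footnote how many entered the first period that way.

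The cost is SAP wording and about four extra tables from onset dates already collected. The downside is a conventional cut-off; events after it still appear in the second-period and 90-day tables. If the unseen index already contains such tables, SAP 11.2.4 need only name them and state the cut-off.

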11.2.5. Laboratory Evaluations

[figure not shown]
The following laboratory tests at local laboratories will be performed at designated visits (See **Table 1: Schedule of Assessments** for timing and frequency):

This document is confidential.

For numeric laboratory results with a preceding ‘<’ or ‘>’, the sign would be ignored and the numeral alone would be considered as the result for summarizing purposes. The listing would, however, display the result as captured in the database.

Summary tables with actual and change from baseline values will be presented for hematology, serum chemistry and coagulation parameters, 

All laboratory data will be listed. Abnormal laboratory values will also be presented in separate listings.

11.2.6. Vital Signs

Vital signs (systolic blood pressure, diastolic blood pressure, pulse rate, respiratory rate, body temperature) will be summarized descriptively by parameter and visit. Similarly, changes from baseline will be summarized. Shift table will be presented at each post-baseline visit showing the number and percentage of subjects with normal, abnormal NCS or abnormal CS at baseline and post-baseline visit, where available. Vital signs data will be listed.

11.2.7. Electrocardiogram (ECG)

 eported and change from baseline values will be summarized by parameter and visit. Shift table for overall ECG interpretation will be presented at each post-baseline visit showing the number and percentage of subjects with normal, abnormal NCS or abnormal CS at baseline and post-baseline visits. ECG results along with abnormalities will be listed.

ECG parameters include heart rate, PR interval, and QT, QT correction Bazett formula (QTcB), QT correction Fridericia formula (QTcF) and a combination of the Q wave, R wave and S wave (QRS) intervals will be presented by normal, abnormal NCS or abnormal CS at each visit in listing.

11.2.8. Physical and Neurological Examination

This document is confidential.

[REDACTED]

A separate listing reporting the status, date of assessment, results and abnormal findings for each body system will be provided for physical examination.

A listing with neurological examination findings will also be provided.

This document is confidential.

SAP text Version: Final v1.0 (30-Jun-2025)

[REDACTED]

Filing requirements: TMF

Page 37 of 55

12. Interim Analyses

No interim analysis is planned for this study.

This document is confidential.

SAP text Version: Final v1.0 (30-Jun-2025)

[REDACTED]
Filing requirements: TMF

Page 38 of 55

13. Data Safety Monitoring Board (DSMB)

An independent DSMB will be established to assess all data (including imaging data) of LT3001 drug product or placebo treatment. The DSMB will review safety and efficacy data when thirtieth treated subjects have completed study procedures on Day 7 or terminated the study prior to Day 7. The DSMB will meet after the data presentation and will issue recommendations relating to safety and study conduct.

[REDACTED]

The DSMB TLFs will be a subset of the TLFs planned for final analysis. Refer to Sections 18, 19 and 20 for list of TLFs.

This document is confidential.

14. Changes from Analysis Planned in Protocol

Any changes to planned analyses, if applicable, will be cited in CSR along with the rationale for the change.

This document is confidential.

SAP text Version: Final v1.0 (30-Jun-2025)

Filing requirements: TMF

Page 40 of 55

15. Reference List

1. Chuang-Stein C. Summarizing laboratory data with different reference ranges in multi-center clinical trials. *Drug Information Journal* 1992; 26(1): 77-84.
2. Chuang-Stein C. Some issues concerning the normalization of laboratory data based on reference ranges. *Drug Information Journal* 2001; 35(1): 153-156.

This document is confidential.

16. Programming Considerations

All statistical computations and construction of tables, listings and figures will be performed using SAS® for Windows Version 9.4 or higher (SAS® Institute Inc., Cary, NC, USA), running on a Windows Server 2012 R2 Standard operating system.

The format of the table shells will be followed as closely as possible; however, in the course of programming and familiarization with the database, some changes may become necessary. All changes will be documented. Major changes will be documented through a formal amendment to this document.

SDTM datasets will be created from the clinical database and external data, following the Study Data Tabulation Model Implementation Guide Version 3.2. Analysis will be based on ADaM datasets created from the SDTM datasets.

The below programming considerations will be followed unless already specified in the above text.

